12.3 Pharmacokinetics**Absorption**

Following single-dose administration of AMRIX 15 mg and 30 mg in healthy adult subjects (n=15), C_{max} , AUC_{0-168} , and $\text{AUC}_{0-\infty}$ increased in an approximately dose-proportional manner from 15 mg to 30 mg. The time to peak plasma cyclobenzaprine concentration (T_{max}) was 7 to 8 hours for both doses of AMRIX.

A food effect study conducted in healthy adult subjects (n=15) utilizing a single dose of AMRIX 30 mg demonstrated a statistically significant increase in bioavailability when AMRIX 30 mg was given with food relative to the fasted state. There was a 35% increase in peak plasma cyclobenzaprine concentration (C_{max}) and a 20% increase in exposure (AUC_{0-168} and $\text{AUC}_{0-\infty}$) in the presence of food. No effect, however, was noted in T_{max} or the shape of the mean plasma cyclobenzaprine concentration versus time profile. Cyclobenzaprine in plasma was first detectable in both the fed and fasted states at 1.5 hours.

When the contents of AMRIX capsules were administered by sprinkling on applesauce, it was found to be bioequivalent to the same dose when administered as an intact capsule.

In a multiple-dose study utilizing AMRIX 30 mg administered once daily for 7 days in a group of healthy adult subjects (n=35), a 2.5-fold accumulation of plasma cyclobenzaprine levels was noted at steady-state.

Metabolism and Excretion

Cyclobenzaprine is extensively metabolized and is excreted primarily as glucuronides via the kidney. Cytochromes P-450 3A4, 1A2, and, to a lesser extent, 2D6, mediate N-demethylation, one of the oxidative pathways for cyclobenzaprine. Cyclobenzaprine has an elimination half-life of 32 hours (range 8-37 hours; n=18); plasma clearance is 0.7 L/min following single dose administration of AMRIX.

Special Populations**Elderly**

Although there were no notable differences in C_{max} or T_{max} , cyclobenzaprine plasma AUC is increased by 40% and the plasma half-life of cyclobenzaprine is prolonged in elderly subjects greater than 65 years of age (50 hours) after dosing with AMRIX compared to younger subjects 18 to 45 years of age (32 hours). Pharmacokinetic characteristics of cyclobenzaprine following multiple-dose administration of AMRIX in the elderly were not evaluated.

Hepatic Impairment

In a pharmacokinetic study of immediate-release cyclobenzaprine in 16 subjects with hepatic impairment (15 mild, 1 moderate per Child-Pugh score), both AUC and C_{max} were approximately double the values seen in the healthy control group. The pharmacokinetics of cyclobenzaprine in subjects with severe hepatic impairment is not known.

13 NONCLINICAL TOXICOLOGY**13.1 Carcinogenesis, Mutagenesis, Impairment of Fertility**

Long-term studies were conducted in CD-1 mice and Sprague-Dawley rats with cyclobenzaprine to evaluate its carcinogenic potential. In an 81-week carcinogenicity study, metastatic hemangiosarcoma was seen in 3 of 21 male mice at 10 mg/kg/day (2 times the MRHD on a mg/m² basis). In a 105-week carcinogenicity study, malignant astrocytoma was seen in 3 of 50 male rats at 10 mg/kg/day (3 times the MRHD on a mg/m² basis). There were no tumor findings in female mice or rats.

Cyclobenzaprine HCl was not mutagenic or clastogenic in the following assays: an *in vitro* Ames bacterial mutation assay, *in vitro* Chinese hamster ovary (CHO) cell chromosomal aberration test, and *in vivo* mouse bone marrow micronucleus assay. Cyclobenzaprine HCl had no effects on fertility and reproductive performance in male or female rats at oral doses up to 20 mg/kg/day (6 times the MRHD on a mg/m² basis).

13.2 Animal Toxicology and/or Pharmacology

In a 67-week study with rats that received cyclobenzaprine at oral doses of 10, 20 or 40 mg/kg/day (3 to 15 times the MRHD on mg/m² basis), there were findings in the liver consisting of midzonal vacuolation with lipidosis for males and midzonal and centrilobular hepatocytic enlargement for females. In addition, there were findings of centrilobular coagulative necrosis. In the higher dose groups, these microscopic changes were seen after 26 weeks and even earlier in rats that died prior to 26 weeks; at lower doses, these changes were not seen until after 26 weeks.

In a 26-week study with Cynomolgus monkeys that received cyclobenzaprine at oral doses of 2.5, 5, 10, or 20 mg/kg/day, one monkey at 20 mg/kg/day (15 times the MRHD on mg/m² basis) was euthanized in week 17. Morbidity for this animal was attributed to findings of chronic pancreatitis, cholecystitis, cholangitis, and focal liver necrosis.

AMRIX® (cyclobenzaprine hydrochloride extended-release capsules)**14 CLINICAL STUDIES**

Efficacy was assessed in two double-blind, parallel-group, active-controlled, placebo-controlled studies of identical design of AMRIX 15 mg and 30 mg taken once daily, between 6:00 and 7:00 PM, cyclobenzaprine 10 mg three times a day, or placebo for 14 days in patients with muscle spasms associated with acute painful musculoskeletal conditions.

There were significant differences in the primary efficacy analysis, the patient's rating of medication helpfulness, between the AMRIX 15 mg group and the placebo group at Days 4 and 14 in one study and between the AMRIX 30 mg group and the placebo group at Day 4 in the second study.

Table 2: Patients' Rating of Medication Helpfulness - Study 1*

	Day 4		Day 14	
	Number of Patients (%)		Number of Patients (%)	
	Placebo (N = 64)	AMRIX 30 mg (N = 64)	Placebo (N = 64)	AMRIX 30 mg (N = 64)
Excellent	1 (2%)	3 (5%)	12 (19%)	15 (23%)
Very Good	5 (8%)	13 (20%)	9 (14%)	19 (30%)
Good	15 (23%)	22 (34%)	10 (16%)	15 (23%)
Fair	24 (38%)	20 (31%)	16 (25%)	10 (16%)
Poor	10 (16%)	5 (8%)	9 (14%)	4 (6%)
Missing	9 (14%)	1 (2%)	8 (13%)	1 (2%)

*Percentages are rounded to the nearest whole percent.

Table 3: Patients' Rating of Medication Helpfulness - Study 2*

	Day 4		Day 14	
	Number of Patients (%)		Number of Patients (%)	
	Placebo (N = 64)	AMRIX 15 mg (N = 63)	Placebo (N = 64)	AMRIX 15 mg (N = 63)
Excellent	1 (2%)	2 (3%)	10 (16%)	13 (21%)
Very Good	10 (16%)	12 (19%)	12 (19%)	21 (33%)
Good	14 (22%)	21 (33%)	13 (20%)	9 (14%)
Fair	16 (25%)	17 (27%)	14 (22%)	10 (16%)
Poor	19 (30%)	6 (10%)	12 (19%)	5 (8%)
Missing	4 (6%)	5 (8%)	3 (5%)	5 (8%)

*Percentages are rounded to the nearest whole percent.

In addition, one of the two studies demonstrated significant differences between the AMRIX 30 mg group and the placebo group in terms of patient-rated relief from local pain due to muscle spasm at Day 4 and Day 8, in patient-rated restriction of movement at Day 4 and Day 8, and in patient-rated global impression of change at Day 4, Day 8, and Day 14.

In both studies, there were no significant treatment differences between the AMRIX treatment groups and the placebo group in physician's global assessment, patient-rated restriction in activities of daily living, or quality of nighttime sleep.

16 HOW SUPPLIED/STORAGE AND HANDLING**16.1 How Supplied**

AMRIX extended-release capsules are available in 15 and 30 mg strengths, packaged in bottles of 60 capsules. AMRIX 15 mg capsules (NDC 63459-700-60) are orange/orange and are embossed in blue ink with "15 mg" on the body, and Cephalon "C" logo, "Cephalon", and a dashed band on the cap. AMRIX 30 mg capsules (NDC 63459-701-60) are blue/red and are embossed in white ink with "30 mg" on the body, and Cephalon "C" logo, "Cephalon", and a dashed band on the cap.

16.2 Storage and Handling

Dispense in a light, light-resistant container as defined in the USP/NF. Store at 25°C (77°F); excursions permitted to 15 - 30°C (59 - 86°F) [see USP Controlled Room Temperature].

17 PATIENT COUNSELING INFORMATION

See FDA-approved patient labeling (Patient Information).

- Instruct patients to swallow AMRIX capsules intact or to sprinkle capsule contents on a tablespoon of applesauce and swallow immediately without chewing.
- Advise patients to stop taking AMRIX and to notify their physician right away if they experience symptoms of an allergic reaction, such as difficulty breathing, hives, swelling of face or tongue, or itching.
- Advise patients that AMRIX should not be taken with MAO inhibitors or within 14 days after their discontinuation.
- Caution patients about the risk of serotonin syndrome with concomitant use of AMRIX and other drugs, such as SSRIs, SNRIs, TCAs, tramadol, bupropion, meperidine, verapamil, or MAO inhibitors. Advise patients of the signs and symptoms of serotonin syndrome [see Warnings and Precautions (5.1)] and instruct patients to seek medical care immediately if they experience these symptoms.

AMRIX® (cyclobenzaprine hydrochloride extended-release capsules)

- Advise patients to stop taking AMRIX and to notify their physician right away if they experience arrhythmias or tachycardia.
- Advise patients that AMRIX may enhance the impairment effects of alcohol. These effects may also be seen if AMRIX is taken with other CNS depressants.
- Caution patients about operating an automobile or other hazardous machinery until it is reasonably certain that AMRIX therapy will not adversely affect their ability to engage in such activities.
- Advise patients to take AMRIX at approximately the same time each day.

TEVA CNS

Distributed By:
Teva Pharmaceuticals USA, Inc.
North Wales, PA 19454

Manufactured By:
Adare Pharmaceuticals, Inc.
Vandalia, OH 45377
AMR-008

US Patent Nos. 7387793, 7754372, 7790199, 7820203, 7829121

AMRIX is a trademark of Teva Pharmaceuticals International GmbH, or its affiliates. © 2004-2016 Teva Pharmaceuticals USA, Inc.
All rights reserved.

Patient Information

**AMRIX® (am-rix)
(cyclobenzaprine hydrochloride)
Extended Release Capsules**

Read this Patient Information before you start taking AMRIX and each time you get a refill. There may be new information. This information does not take the place of talking with your healthcare provider about your medical condition or your treatment.

What is AMRIX?

AMRIX is a prescription medicine used along with rest and physical therapy to help treat muscle spasm due to acute, painful musculoskeletal problems.

AMRIX should only be used for up to 2 or 3 weeks. It is not known if AMRIX is effective when used for longer periods.

It is not known if AMRIX is safe and effective in children.

Who should not take AMRIX?

Do not take AMRIX if you:

- are allergic to cyclobenzaprine or any of the ingredients in AMRIX. See the end of this Patient Information leaflet for a complete list of ingredients in AMRIX.

Talk to your healthcare provider or get medical help right away if you have symptoms of an allergic reaction such as:

- difficulty breathing
- hives
- swelling of your face or tongue
- itching
- are taking certain antidepressants, known as monoamine oxidase (MAO) inhibitors or it has been 14 days or less since you stopped taking a MAO inhibitor. Ask your healthcare provider or pharmacist for a list of these medicines if you are not sure.
- have had a recent heart attack
- have heart rhythm problems (arrhythmias)
- have heart failure
- have an overactive thyroid (hyperthyroidism)

Talk to your healthcare provider before taking this medicine if you have any of the conditions listed above.

What should I tell my healthcare provider before taking AMRIX?**Before you take AMRIX, tell your healthcare provider if you:**

- have a history of eye problems including glaucoma
- have heart problems or have had a heart attack
- have liver problems
- have trouble emptying your bladder (urinary retention)
- are pregnant or plan to become pregnant. It is not known if AMRIX will harm your unborn baby.

AMRIX® (cyclobenzaprine hydrochloride extended-release capsules)

- are breastfeeding or plan to breastfeed. It is not known if AMRIX passes into your breast milk. You and your healthcare provider should decide if you will take AMRIX or breastfeed.

AMRIX may affect the way other medicines work, and other medicines may affect how AMRIX works.

Tell your healthcare provider about all the medicines you take including prescription and non-prescription medicines, vitamins, and herbal supplements.

Especially tell your healthcare provider if you take:

- a medicine to treat depression, mood, anxiety, psychotic or thought disorders
- a pain medicine called tramadol or meperidine
- barbiturates or other medicines that depress your central nervous system (CNS depressants)
- a medicine that prevents nerve impulses (anticholinergic medicines)
- a medicine to help quit smoking called bupropion
- a blood pressure medicine called verapamil

Ask your doctor or pharmacist if you are not sure if you take any of the medicines listed above.

Know the medicines you take. Keep a list of your medicines and show it to your healthcare provider or pharmacist when you get a new medicine.

How should I take AMRIX?

- Take AMRIX exactly as your healthcare provider tells you to take it.
- Your healthcare provider will tell you how much AMRIX to take and when to take it.
- Your healthcare provider may change your AMRIX dose if needed.
- Take AMRIX around the same time every day.
- AMRIX should only be taken for short periods (up to two or three weeks).
- If you take too much AMRIX, call your doctor or go to the nearest hospital emergency room right away.

What should I avoid while taking AMRIX?

You should not drink alcohol until you know how AMRIX affects you. Taking AMRIX with alcohol or other medicines that depress your central nervous system can slow your thinking and physical response times.

Do not drive, operate machinery, or do other dangerous activities until you know how AMRIX affects you.

What are the possible side effects of AMRIX?

AMRIX may cause serious side effects that may lead to heart attack or stroke. Call your healthcare provider right away or go to the nearest hospital emergency room if you have:

- irregular or abnormal heartbeats (arrhythmias)
- fast heartbeat (tachycardia)

Serotonin syndrome is a serious medical condition that may happen when AMRIX is taken with certain other medicines. Call your healthcare provider right away or go to the nearest hospital emergency room if you become severely ill and have some or all of these symptoms:

- agitation, hallucinations, coma or other changes in mental status
- coordination problems or muscle twitching (overactive reflexes)
- fast heartbeat, high or low blood pressure
- sweating or fever
- nausea, vomiting, or diarrhea
- muscle stiffness or tightness

The most common side effects of AMRIX include:

- dry mouth
- dizziness
- fatigue
- constipation
- nausea
- upset stomach
- drowsiness

Tell your healthcare provider if you get any side effect that bothers you or that does not go away.

AMRIX® (cyclobenzaprine hydrochloride extended-release capsules)

These are not all the possible side effects of AMRIX. For more information, ask your healthcare provider or pharmacist. Call your healthcare provider for medical advice about side effects. You may report side effects to FDA at [name].

How should I store AMRIX?

- Store AMRIX at room temperature, between 59° F to 86° F (15°C to 30°C).
- Keep AMRIX in a tightly closed container, and keep AMRIX out of light.
- **Keep AMRIX and all medicines out of the reach of children.**

General information about the safe and effective use of AMRIX. Medicines are sometimes prescribed for purposes other than those listed in a Patient Information leaflet. Do not use AMRIX for a condition for which it was not prescribed. Do not give AMRIX to other people, even if they have the same symptoms you have. It may harm them.

This Patient Information leaflet summarizes the most important information about AMRIX. If you would like more information, talk with your healthcare provider. You can ask your healthcare provider or pharmacist for information about AMRIX that is written for healthcare professionals.

For more information, go to www.AMRIX.com or call [name].

What are the ingredients in AMRIX?

Active Ingredient: cyclobenzaprine hydrochloride USP

Inactive Ingredients: diethyl phthalate NF, ethylcellulose NF (Ethocel Standard 10 Premium), gelatin, Opadry® Clear YS-1-7006, sugar spheres NF (20-25 mesh), and titanium dioxide.

AMRIX 15 mg capsules also contain: D&C yellow #10, FD&C green #3, and FD&C red #40.

AMRIX 30 mg capsules also contain: FD&C blue #1, FD&C blue #2, FD&C red #40, and FD&C yellow #6.

Distributed By:

Teva Pharmaceuticals USA, Inc.
North Wales, PA 19454

Manufactured By:
Adare Pharmaceuticals, Inc.
Vandalia, OH 45377

AMRPL-003

Revised May 2016

AMRIX is a trademark of Teva Pharmaceuticals International GmbH, or its affiliates.

© 2004-2016 Teva Pharmaceuticals USA, Inc.

All rights reserved.

AMR-40470

1. OVERVIEW

This Statistical Analysis Plan (SAP) describes the planned analysis and reporting for protocol TNX-CY-P303: A 12-Week Open-Label Extension Study to Evaluate TNX-102 SL Taken Daily at Bedtime in Patients with PTSD (17MAR2017); Amendment 1, Dated 31MAR2017.

The structure and content of this SAP provides sufficient detail to meet the requirements identified by FDA, European Medicines Agency (EMA), and International Council for Harmonization (ICH) of Technical Requirements for Registration of Pharmaceuticals for Human Use: Guidance on Statistical Principles in Clinical Trials. All work planned and reported for this SAP will follow internationally accepted guidelines, published by the American Statistical Association and the Royal Statistical Society, for statistical practice.

The planned analyses identified in this SAP may be included in clinical study reports (CSRs), regulatory submissions, or future manuscripts. Also, post-hoc exploratory analyses not necessarily identified in this SAP may be performed to further examine study data. Any post-hoc, or unplanned exploratory analysis performed will be clearly identified as such in the final CSR.

- [REDACTED]
- [REDACTED]
- [REDACTED]
- [REDACTED]

The reader of this SAP is encouraged to also read the clinical protocol, and other identified documents, for details on the planned conduct of this study. Operational aspects related to collection and timing of planned clinical assessments are not repeated in this SAP unless relevant to the planned analysis.

2. STUDY OBJECTIVES AND ENDPOINTS

2.1 Study Objectives

2.1.1 Primary Objective

The primary objective of the study is to evaluate the safety of TNX-102 SL taken daily at bedtime over an additional 12 weeks in patients with PTSD who have completed a double-blind lead-in study.

2.1.2 Secondary Objectives

The secondary objective is to evaluate the safety of TNX-102 SL 5.6 mg taken at bedtime over 12 weeks of treatment.

2.2 Study Endpoints

2.2.1 Efficacy Endpoints

Comparisons will be made at each study week of data collection to both the baseline of this study (P303) and the baseline from the double-blind study (P301) and described in [section 7.1](#).

Efficacy endpoints include:

- Change from both baselines in the total CAPS-5 score
- Proportion of patients with a CGI-I score of “very much improved” or “much improved”
- from both baselines
- Change from both baselines in the SDS total score
- Change from both baselines in the individual items assessed using the SDS
- Change from both baselines in patients’ quality of sleep using the PROMIS Sleep Disturbance scale
- Change from both baselines in CAPS-5 symptom cluster subscores
- Proportion of patients with a $\geq 50\%$ improvement from baseline (both baselines) in total
- CAPS-5 score
- Change from both baselines in BDI-II score

2.2.2 Safety Endpoints

Safety will be assessed by:

- Adverse events (AE) and serious AEs (SAEs) throughout the entire duration of the study, including detailed assessment of AEs involving the oral cavity.
- Changes from both baselines in clinical laboratory test results.
- Changes from both baselines in vital signs and weight.
- Change from both baselines in BDI-II.
- Suicidal ideation or behavior as reported on the Columbia Suicide Severity Rating Scale (C-SSRS).

3. OVERALL STUDY DESIGN AND PLAN

This is a 12-week, multicenter, open-label extension study designed to accumulate additional safety exposure and efficacy data with daily bedtime dosing of TNX-102 SL 5.6 mg (2 x 2.8mg tablets) in patients with PTSD. This study will be conducted at approximately 35 sites in the United States (US).

Patients who have completed participation in a Phase 3, randomized, double-blind, placebo controlled study comparing TNX-102 SL 5.6 mg versus placebo for the treatment of PTSD will be eligible. This extension study consists of 5 visits, including the Screening/Baseline visit (which is anticipated to be the same as the primary outcome visit in the double-blind lead-in study), a telephonic visit at week 2, and in-clinic visits after 4, 8 and 12 weeks of treatment (Visits 3-5). The total treatment duration of this study will be 12 weeks. Therefore, the maximum total duration of continuous treatment with TNX-102 SL could be approximately 24 weeks for those patients assigned to active study drug in the lead-in study.

Patient data collected at the Week 12 visit in the lead-in study will be used as one of the defined baselines for this study. There is no need to repeat assessments at Visit 1 for this study, if they were collected in the lead-in study and patients enroll and initiate study treatment within fourteen days of completing the lead-in study. After the patient has completed his/her participation in the lead-in study and has consented to participate in this open-label extension study, patients will be dispensed a 4-week supply of open-label TNX-102 SL tablets and will be instructed to take the study drug sublingually daily at bedtime, starting on the evening of Visit 1. A phone visit will be completed after 2 weeks of treatment and patients will return to the study center for safety and efficacy assessments at Weeks 4, 8, and 12 (or early termination). At the Weeks 4 and 8 visits patients will return their TNX-102 SL medication and will receive another 4-week supply. Patients will be allowed to take medications deemed appropriate by their health care providers to manage their PTSD and other conditions, including currently approved PTSD therapies.

3.1 Selection of Study Population

For a complete list of inclusion and exclusion criteria please refer to the initial protocol issued March 17, 2017 and Amendment 1, dated March 31, 2017.

3.2 Method of Treatment Assignment and Randomization

All patients will be assigned to TNX-102 SL, 5.6 mg regardless of which treatment arm they were randomized to in the lead-in study. No patients or site personnel will know what the prior treatment was in the double-blind lead-in study.

Throughout this document, when describing analyses performed by treatment group, this will refer to the treatment that the subject was randomized to in the double-blind lead-in study.

4. ANALYSIS AND REPORTING

4.1 Final Analysis

All final, planned analyses will be performed after the last participant has completed all study assessments, all relevant study data have been processed and integrated into the analysis database, and the database has been locked

Any post-hoc, exploratory analyses completed to support planned study analysis, which were not identified in this SAP, will be documented and reported in appendices to the CSR. Any results from these unplanned analyses (post-hoc) will also be clearly identified in the text of the CSR.

5. SAMPLE SIZE DETERMINATION

No sample size calculations were made for this study as it is a follow-on, open-label study. The sample size for this study will depend upon the number of patients who complete the lead-in study, remain eligible for entry, and indicate willingness to participate in this extension study.

6. ANALYSIS POPULATIONS

The following analysis populations are planned for this study:

- **Safety Population (SAFETY):** All participants who receive at least 1 dose of study drug. Participants who are issued study drug, but return 100% of it (i.e., none consumed) will be excluded from the safety population; likewise, participants that have no follow up following receipt of study drug to indicate they took drug are excluded. All safety analyses and demographic/baseline characterization will be performed using this population.

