The primary objective of the study is to evaluate the safety of treatment with TNX-102 SL 5.6 mg for an additional 12 weeks in patients with PTSD who have completed a double-blind lead-in study. Safety will be assessed by the monitoring and recording of AEs, clinical laboratory tests, vital signs,

the monitoring of suicidality using the Columbia Suicide Rating Scale (C-SSRS) scale and the monitoring of depressive symptoms using the Beck Depression Inventory (BDI-II).

Efficacy will continue to be assessed during 12 weeks of open-label treatment with the Clinician-Administered PTSD Scale for DSM-5 (CAPS-5), the Clinician Global Impression of Improvement (CGI-I), the Sheehan Disability Scale (SDS) and the Patient Reported Outcomes Measurement Information System (PROMIS) sleep disturbance scale.

Statistics

Analysis Population:

The Safety Population will comprise all patients who receive at least 1 dose of study drug.

Treatment Groups:

As an extension of a double-blind study, two treatment groups will be defined as follows:

- TNX-102 SL /TNX-102 SL treatment group: patients who received TNX-102 SL in the double-blind lead-in study and then continued to receive TNX-102 SL in the extension study
- Placebo/TNX-102 SL treatment group: patients who received placebo in the double-blind study and then received TNX-102 SL in the extension study

Patients and site personnel will not be informed concerning treatment assignments in the lead-in study, thus there will be a blinded crossover to active therapy in the extension study.

Baseline:

Baseline will be defined in two different ways as follows: (1) as the last measurement obtained prior to randomization in the double-blind lead-in study (i.e., the original baseline from the lead-in study); and (2) as the measurement obtained at the final primary outcome visit in the double-blind lead-in study and prior to enrollment into the P303 extension study (i.e., the measurement from the final visit of the double-blind lead-in study, which is the same as P303 Visit 1).

Safety Analyses:

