A death occurring during the study or reported to the Investigator after study participation (no required post-study time limit) must be reported to Tonix or its designee(s) immediately, whether or not it is considered treatment-related. Initial SAE reports must be followed by detailed descriptions. These should include copies of hospital case records and other documents when requested. The CRO will confirm via email or facsimile when it has received SAE documentation. If such confirmation is not received at the site in a timely manner, it is then the responsibility of the site to contact the CRO to ensure that the SAE documentation was indeed received by the CRO.

The Investigator or other study personnel must immediately inform one of the Tonix Medical Monitors by phone or email of any AE considered serious or otherwise significant, as described above. **In addition, a completed SAE report form must be submitted to [REDACTED]
[REDACTED] within 24 hours of the site's initial awareness of the event.**

Contact information for the Medical Monitors is provided below:

For questions pertaining to the reporting of SAEs or the completion of SAE documentation, site personnel should call [REDACTED]

The investigator, or the sponsor or designee in the case of a central Institutional Review Board (IRB), also must notify the EC (Ethics Committee)/IRB of the occurrence of the SAE, in writing, as soon as is practicable and in accordance with local law. A copy of this notification must be provided to Tonix or its designee.

In the event of an SAE that meets the criteria for expedited reporting, an Investigational New Drug (IND) Safety Report will be prepared for submission to the FDA.

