10. SAFETY AND TOLERABILITY ANALYSIS

The safety analysis will be run on the Safety population. The analysis of safety assessments in this study will include summaries of the following safety and tolerability data collected for each participant:

- Adverse Events

- Clinical Laboratory Investigations
- C-SSRS
- Vital Signs
- Visual Examinations of Oral Cavity
- BDI-II

Summaries of continuous parameters will include raw values and change from baseline, as appropriate. Listings of safety data will also be presented.

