10.1.2 Serious Adverse Events

A summary of incidence rates (frequencies and percentages) of SAEs by treatment group, SOC, and preferred term will be prepared for the Safety population. A data listing of SAEs will also be provided, displaying details of the event(s) captured on the CRF.

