10.1.3 Deaths

A listing of deaths will also be provided for the Safety Population.

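### SAP 6 treats unknown intake as non-use, so an early death or SAE with dosing never confirmed can be missing from the SAE table and the deaths listing

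*SAP*

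**What the plan says.** The protocol Synopsis states: "The Safety Population will comprise all patients who receive at least 1 dose of study drug". It does not say what to do when intake is unknown.

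SAP 6 repeats that definition and adds two exclusions. The first removes patients who return every tablet. The second reads: "participants that have no follow up following receipt of study drug to indicate they took drug are excluded". It then sets the reach of the population: "All safety analyses and demographic/baseline characterization will be performed using this population".

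Two later outputs are tied to it by name:

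- SAP 10.1.2: "A summary of incidence rates (frequencies and percentages) of SAEs by treatment group, SOC, and preferred term will be prepared for the Safety population".
- SAP 10.1.3: "A listing of deaths will also be provided for the Safety Population".

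Other outputs are not tied to it. SAP 10.1 has the AE listings show every AE, the SAE data listing in SAP 10.1.2 states no population limit, and the disposition table in SAP 8.1 covers everyone with data in the database. SAP 12 records only the renumbering of Day 0 to Day 1 and does not mention the population rule.

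**The concern.** The two exclusions in SAP 6 differ in kind. Returning all tablets is positive evidence that no drug was taken. Having no follow-up that shows intake is only an absence of evidence, and that absence can be related to outcome: intake may be hard to establish in a patient who dies or breaks off contact soon after Visit 1.

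Safety is the primary objective. Deaths and SAEs are few, so a single case can decide whether a row reads zero or one. A death reported by a relative or hospital, with the bottles never recovered, must reach the sponsor under Protocol 11.3 (a death "must be reported to Tonix or its designee(s) immediately, whether or not it is considered treatment-related"). Yet it could be left out of the one output devoted to deaths and of the SAE counts. Any such omission makes the drug look safer.

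**Working it through.** The documents give no sample size, early-loss rate or event rate bearing on this point, so there is no plan figure to reproduce. The check has three parts.

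**1. When could intake first be shown?**

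- Protocol 9.1.4: dosing starts on the evening of Visit 1.
- Protocol 9.2: the first scheduled contact is a telephone call on Day 14 ± 3, so at latest 14 + 3 = Day 17. Compliance is taken by verbal report.
- Protocol 9.3: the first tablet count is on Day 28 ± 7, so at latest 28 + 7 = Day 35.

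A patient lost before the call has no scheduled contact that could show dosing.

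**2. Do the SAP's exposure rules supply the evidence?** SAP 11.2 gives duration = last dose date − first dose date + 1. For a patient lost to follow-up or with no last dose date, it sets that date to the day before the last clinic visit attended. If Visit 1 (day v) is the only clinic visit and the first dose is that evening:

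- last dose date = v − 1
- first dose date = v
- duration = (v − 1) − v + 1 = 0 days

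The same section leaves a period with unreturned bottles out of exposure and compliance. These rules therefore give no evidence of dosing. The patient stays in the population only if some other report says drug was taken, and the SAP does not say whether a death or SAE report counts as follow-up for this purpose.

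**3. Where would the event be shown?**

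| Output | Stated scope | Case with intake unknown |
|---|---|---|
| SAE incidence table (SAP 10.1.2) | Safety Population | Missing |
| Deaths listing (SAP 10.1.3) | Safety Population | Missing |
| AE data listings (SAP 10.1) | All AEs | Should appear |
| SAE data listing (SAP 10.1.2) | No limit stated | Should appear |
| Disposition (SAP 8.1) | All in database | Patient appears |

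**Illustration of size.** N dispensed patients is an assumption. One case is either excluded, giving 0/(N − 1), or kept, giving 1/N. The limits are exact (Clopper-Pearson) two-sided 95% upper limits.

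| Assumed N | Excluded: upper limit | Kept: rate, upper limit | Shortfall in upper limit |
|---|---|---|---|
| 50 | 0/49: 7.25% | 2.00%, 10.65% | 1 − 7.25/10.65 = 32% |
| 100 | 0/99: 3.66% | 1.00%, 5.45% | 1 − 3.66/5.45 = 33% |
| 200 | 0/199: 1.84% | 0.50%, 2.75% | 1 − 1.84/2.75 = 33% |
| 300 | 0/299: 1.23% | 0.33%, 1.84% | 1 − 1.23/1.84 = 33% |

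The SAP plans frequencies and percentages for SAEs and specifies no confidence interval for them. The limits only give a sense of scale.

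**The case against.** The strongest reply is that the exclusion is narrow and the event does not vanish. Much of this stands.

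- **A reader might infer that the event is lost from the report.** The documents do not support that. A death is an SAE under Protocol 11.3, and neither the AE listings nor the SAE data listing is expressly limited to the Safety Population. The exposure is the SAE table counts and the deaths listing.
- **A reader might infer that any early death or SAE is excluded.** It is not. Protocol 11.3 requires detailed follow-up of SAE reports, with hospital records on request, and a report that documents dosing would keep the patient in. A hospitalised survivor can be asked. The rule applies only where intake stays unknown. Nothing in the documents says how often patients miss the Week 2 call.
- **A reader might call this an undeclared contradiction of the protocol.** That is arguable. The protocol counts patients who took a dose, not all those dispensed drug, and is silent on unknown intake. The SAP had to set some rule.
- **Suicidality data are less exposed.** The Week 2 call pairs the C-SSRS with a compliance question, and Weeks 4 and 8 pair it with drug accountability.
- **The SAP's cautious imputations in section 7.3.1** (missing severity becomes severe, missing relationship becomes related) concern events already recorded, so they are an imperfect comparison.

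What does not fall away is that a rule the plan states, not a missing detail, removes such a case from the SAE table and the deaths listing.

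**Conclusion.** The point holds in this limited form. SAP 6 resolves unknown intake as non-use, and the SAE table and deaths listing inherit that choice. A death or SAE soon after dispensing, with intake never confirmed, can be missing from both while still appearing in the AE and SAE data listings and, for the patient, in disposition. Such cases are probably few, and their number cannot be derived from the documents.

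The illustration rests on an assumed N and on one such case occurring. On those terms the rate goes from 0% to between 0.33% (N = 300) and 2.00% (N = 50), and the unplanned upper limit is about one third too low. A reader might put that shortfall at one half. One half is roughly how far the limit rises when the case is restored (for N = 100, 5.45/3.66 = 1.49), not the shortfall against the correct limit.

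This is a cheap improvement worth making because safety is the primary objective. It is not a defect that undermines the study.

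**What to change.** 1. **SAP 6:** exclude only patients with documented non-use (all tablets returned, or recorded as never having dosed). Count every other dispensed patient as dosed, whether or not an event was reported. Admitting unknown-intake patients only when they have an event would select on outcome and inflate the rates. When the first dose date is unknown, take the evening of Visit 1, so that newly emergent status can be assigned.
2. **SAP 10.1.2 and 10.1.3:** state that the SAE and deaths listings cover all dispensed patients, with unconfirmed intake flagged. For the SAE listing this mainly makes explicit what the present text leaves open.
3. **SAP 8.1:** report the number dispensed drug with unknown intake.
4. **SAP 12:** note the population rule beside the protocol definition.

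The cost is SAP wording, one flag and one disposition row, with no new data. The downside is that a few patients who never dosed may enter the denominator and slightly lower the percentages for common AEs. A sensitivity table excluding the unknown-intake patients would show by how much. Under SAP 11.2 some of these patients would have a computed duration of 0 days, so the exposure table should mark their exposure as unknown.
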